14. APPENDICES

**Appendix 1:
TOXICITY GRADING TABLE**

TABLE FOR GRADING SEVERITY OF ADULT ADVERSE EXPERIENCES©

**ACTG 285
DIVISION OF AIDS**

ABBREVIATIONS: Abbreviations used in the table:

ULN =	Upper Limit of Normal
LLN =	Lower Limit of Normal
Rx =	Therapy
Req =	Required
Mod =	Moderate
IV =	Intravenous
ADL =	Activities of Daily Living
Dec =	Decreased

ESTIMATING SEVERITY OF GRADE

For abnormalities NOT found elsewhere on the Toxicity Table use the scale below to estimate grade of severity:

GRADE 1 Mild

Transient or mild discomfort; no limitation in activity; no medical intervention/ therapy required

GRADE 2 Moderate

Mild or moderate limitation in activity - some assistance may be needed; no or minimal medical intervention/therapy required

GRADE 3 Severe

Marked limitation in activity, some assistance usually required; medical intervention/therapy required, hospitalisations possible

GRADE 4 Life-threatening

Extreme limitation in activity, significant assistance required; significant medical intervention/therapy required, hospital or hospice care probable

Appendix 1:
ATCG Toxicity Grading Table

SERIOUS OR LIFE-THREATENING AE's

ANY clinical event deemed by the clinician to be serious or life-threatening should be considered a grade 4 adverse experience. Clinical events considered to be serious or life-threatening include, but are not limited to:

seizures, coma, tetany, diabetic ketoacidosis, disseminated intravascular coagulation, diffuse petechiae, paralysis, acute psychosis

PARAMETER	GRADE MILD	GRADE MODERATE	GRADE SEVERE	GRADE POTENTIALLY LIFE-THREATENING
HEMATOLOGY				
Hemoglobin	8.0g/dL - 9.4g/dL	7.0g/dL - 7.9g/dL	6.5g/dL - 6.9g/dL	< 6.5g/dL
Absolute Neutrophil Count	1000 -1500/mm ³	750 -999/mm ³	500 -749/mm ³	< 500/mm ³
Platelets	75,000 - 99,000/mm ³	50,000 - 74,999/mm ³	20,000 - 49,999/mm ³	< 20,000/mm ³
Prothrombin Time (PT)	> 1.0 - 1.25 X ULN	> 1.25 - 1.5 X ULN	> 1.5 - 3.0 X ULN	> 3.0 X ULN
BT	> 1.0 - 1.66 X ULN	> 1.66 - 2.33 X ULN	> 2.33 - 3.0 X ULN	> 3.0 X ULN
Methemoglobin	5.0 - 10.0%	10.0 - 15.0%	15.0 - 20.0%	> 20.0%
CHEMISTRIES				
SODIUM				
Hyponatremia	130 - 135meq/L	123 - 129meq/L	116 - 122meq/L	< 116meq/L
Hypernatremia	146 - 150meq/L	151 - 157meq/L	158 - 165meq/L	> 165meq/L
POTASSIUM				
Hyperkalemia	5.6 - 6.0meq/L	6.1 -6.5meq/L	6.6 - 7.0meq/L	> 7.0meq/L
Hypokalemia	3.0 - 3.4meq/L	2.5 - 2.9meq/L	2.0 - 2.4meq/L	< 2.0meq/L
PHOSPHATE				
Hypophosphatemia	2.0 - 2.4 mg/dL	1.5 - 1.9 mg/dL	1.0 - 1.4 mg/dL	< 1.0 mg/dL
CALCIUM				
Hypocalcemia	7.8 - 8.4 mg/dL	7.0 - 7.7 mg/dL	6.1 - 6.9 mg/dL	< 6.1 mg/dL
Hypercalcemia	10.6 - 11.5 mg/dL	11.6 - 12.5 mg/dL	12.6 - 13.5 mg/dL	> 13.5 mg/dL
MAGNESIUM				
Hypomagnesemia	1.2 - 1.4 meq/L	0.9 - 1.1 meq/L	0.6 - 0.8 meq/L	< 0.6 meq/L
BILIRUBIN	> 1.0 - 1.5 x ULN	> 1.5 - 2.5 x ULN	> 2.5 - 5.0 x ULN	> 5.0 x ULN
GLUCOSE				
Hypoglycemia	55 - 64 mg/dL	40 - 54 mg/dL	30 - 39 mg/dL	< 30 mg/dL
Hyperglycemia (nonfasting and no prior diabetes)	116 - 160 mg/dL	161 - 250 mg/dL	251 - 500 mg/dL	> 500 mg dL
Triglycerides	-----	400 - 750 mg/dL	751 - 1200 mg/dL	> 1200 mg/dL
Creatinine	> 1.0 - 1.5 x ULN	> 1.5 -3.0 x ULN	> 3.0 -6.0 x ULN	> 6.0 x ULN
URIC ACID				
Hyperuricemia	7.5 - 10.0 mg/dL	10.1 - 12.0 mg/dL	12.1 - 15.0mg/dL	>15.0mg/dL

Appendix 1: ATCG Toxicity Grading Table

PARAMETER	GRADE MILD	GRADE MODERATE	GRADE SEVERE	GRADE POTENTIALLY LIFE-THREATENING
LIVER TRANSAMINASE (LFTs)				
AST (SGOT)	1.25 - 2.5 x ULN	2.5 - 5.0 x ULN	5.0 - 10.0 x ULN	> 10.0 x ULN
ALT (SGPT)	0.25 - 2.5 x ULN	2.5 - 5.0 x ULN	5.0 - 10.0 x ULN	> 10.0 x ULN
GGT	1.25 - 2.5 x ULN	2.5 - 5.0 x ULN	5.0 - 10.0 x ULN	> 10.0 x ULN
Alkaline Phosphatase	1.25 - 2.5 x ULN	2.5 - 5.0 x ULN	5.0 - 10.0 x ULN	> 10.0 x ULN
PANCREATIC ENZYMES				
Amylase	> 1.0 - 1.5 x ULN	> 1.5 - 2.0 x ULN	> 2.0 - 5.0 x ULN	> 5.0 x ULN
Pancreatic amylase	> 1.0 - 1.5 x ULN	> 1.5 - 2.0 x ULN	> 2.0 - 5.0 x ULN	> 5.0 x ULN
Lipase	> 1.0 - 1.5 x ULN	> 1.5 - 2.0 x ULN	> 2.0 - 5.0 x ULN	> 5.0 x ULN
CARDIOVASCULAR				
Cardiac Arrhythmias	-----	Asymptomatic; transient dysrhythmia, no Rx req	Recurrent/persistent dysrhythmia; Rx req	Unstable dysrhythmia; symptomatic; hospitalisation and Rx req
Hypertension	Transient increase > 20mmHg; no Rx	Recurrent; chronic increase > 20mmHg; Rx req	Acute Rx req; outpatient, hospitalisation possible	Hospitalisation req
Hypotension	Transient orthostatic hypotension; no RX	Symptoms correctable with oral fluid Rx	IV fluid req; no hospitalisation req	Hospitalisation req
Pericarditis	Minimal effusion	Mild/mod asymptomatic effusion, no RX	Symptomatic effusion, pain, EKG changes	Tamponade OR pericardiocentesis OR surgery req
Hemorrhage, blood	-----	Mildly symptomatic; no Rx req	gross blood loss OR 1-2 units transfused	Massive blood loss OR > 2 units transfused
GASTROINTESTINAL				
Nausea	Mild Or transient; reasonable intake maintained	Mod discomfort OR intake decreased for > 3 days	Severe discomfort OR minimal intake for ≥3 days	Hospitalisation req
Vomiting	Mild OR transient; 2-3 episodes per day OR mild vomiting lasting < 1 week	Mod OR persistent; 4-5 episodes per day; OR vomiting lasting > 1 week	severe vomiting of all food/fluids in 24 hours OR orthostatic hypotension OR IV Rx req	Hypotensive shock OR hospitalisation req for IV Rx
Diarrhea	Mild OR transient; 3-4 loose stools per day OR mild diarrhea lasting < 1 week	Mod OR persistent 5-7 loose stools per day OR diarrhea lasting ≥ 1 week	Bloody diarrhea OR orthostatic hypotension OR > 7 loose stools/day OR IV Rx req	Hypotensive shock OR hospitalisation req
Oral Discomfort/Dysphagia	Mild discomfort; no difficulty in swallowing	Difficulty swallowing but able to eat drink fluids	Unable to swallow solids; IV fluids req	Unable to drink fluids; severe distension with vomiting

Appendix 1: ATCG Toxicity Grading Table

PARAMETER	GRADE MILD	GRADE MODERATE	GRADE SEVERE	GRADE POTENTIALLY LIFE-THREATENING
RESPIRATORY				
Cough	Transient; no Rx	Treatment associated cough; inhaled bronchodilator	Uncontrolled cough; systemic Rx req	
Bronchospasm	Acute transient; no Rx; FEV1 < 80% - 70% (or peak flow)	Rx req; normalizes with bronchodilator; FEV1 50% - < 70% (or peak flow)	No normalization with bronchodilator; (or FEV1 25% - < 50% or peak flow)	Cyanosis OR retractions; FEV1 < 25% (or intubated peak flow)
Dyspnea	Dyspnea on exertion	Dyspnea with normal activity	Dyspnea at rest	Dyspnea req O ₂ Rx
NEUROLOGIC				
Neuro-cerebellar	Slight incoordination OR dysdiadochokinesia	Intention tremor OR dysmetria OR slurred speech OR nystagmus	Ataxia requiring assistance to walk or arm incoordination interfering with ADLs	Unable to stand
Neuro-psych/mood			Severe mood changes req medical intervention	Acute psychosis req hospitalisation
Paresthesia	Mild discomfort; no Rx req (burning, tingling etc)	Mod discomfort; Rx req with symptomatic improvement	Severe discomfort OR non-narcotic analgesia req	Incapacitating OR narcotic analgesia req; not responsive to non-narcotic analgesia
Neuro-motor	Mild weakness in muscles of feet but able to walk and/or mild decrease in r flexes and/or loss of previously present reflex or development of hyperreflexia and/or unable to do deep knee bends due to weakness	Mod weakness in feet (unable to walk on heels and/or toes); mild weakness in hands, still able to do most tasks	Marked distal weakness (unable to dorsiflex toes or foot drop) and proximal weakness e.g., in hands interfering with ADLs and/or req assistance to walk and/or unable to rise from chair unassisted	Confined to bed or wheel chair because of muscle weakness
Neuro-sensory	Mild impairment (dec sensation e.g., vibratory, pinprick, hot/cold in great toes) in focal area or symmetrical distribution	Mod impairment (mod dec sensation e.g., vibratory, pinprick, hot/cold to ankles) and/or joint position or mild impairment that is not symmetrical	Severe impairment (dec or loss of sensation to knees or wrists) or loss of sensation of at least mod degree in multiple different body areas (i.e., upper and lower extremities)	Sensory loss involves limbs and trunk

OZ1: Clinical Protocol OZ1-HV1-202 Amendment 4; 07 June 2017

Appendix 1: ATCG Toxicity Grading Table

PARAMETER	GRADE MILD	GRADE MODERATE	GRADE SEVERE	GRADE POTENTIALLY LIFE-THREATENING
URINALYSIS				
Proteinuria - spot urine 24 hr urine	+1 200mg - 1g loss/day OR < 0.3% OR < 3 g/L	2-3 + 1-2 g loss/day OR 0.3-1.0% OR 3- 10g/L	+4 2 - 3.5g loss/day OR >1.0% OR > 10g/L	Nephrotic syndrome Nephrotic syndrome OR > 3.5g loss/day
Gross Hematuria	Microscopic only	Gross; no clots	Gross plus clots	Obstructive
MISCELLANEOUS				
Fever (oral > 12 hours)	37.7 - 38.5°C OR 100.0 - 101.5°F	38.6 - 39.5°C OR 101.6 - 102.9°F	39.6 40.5°C OR 103 -105°F	> 40.5°C OR > 105°F
Headache	Mild; no Rx req	Mod; or non- narcotic analgesia Rx	Severe; OR responds to initial narcotic Rx	Intractable; OR req repeated narcotic Rx
Allergic Reaction	Pruritus without	Localized urticaria	Generalised urticaria; angioedema	Anaphylaxis
Cutaneous/Rash/Der matitis	Erythema, pruritus	Diffuse maculopapular rash OR dry desquamation	Vesiculation OR moist desquamation OR ulceration	ANY ONE: mucous membrane involvement, suspected Stevens- Johnson (TEN), erythema multiforme, necrosis req surgery, exfoliative dermatitis
Local Reaction (2° parenteral Rx)	Erythema	Induration < 10mm OR inflammation OR phlebitis	Induration >10mm OR ulceration	Necrosis of skin
Fatigue	Normal activity reduced < 25%	Normal activity reduced 25-50%	Normal activity reduced >50%; cannot work	Unable to care for self

Appendix 2:[†]
TELEPHONE FOLLOW-UP QUESTIONNAIRE
FOR SEMI-ANNUAL, ANNUAL, OR END-OF-STUDY REVIEW OF CLINICAL HISTORY

Instructions for Interviewer: This interview will be conducted over the phone by a study investigator only if a patient is unable to be reviewed in the clinic.

SUBJECT NAME:

Date of Birth: |__|_| - |__|_|_|_| - |__|_|
 DD MMM YY

INTERVIEWER SIGNATURE:

Date of Interview: |__|_| - |__|_|_|_| - |__|_|
 DD MMM YY

Study Physician: Circle all appropriate answers for PARTS A, B & C. If respondent answers 'yes' to any of the PART A questions, complete sub-sections and add any additional comments.

All questions refer to the time since the since the last study visit or interview.

PART A: Targeted Review of Clinical History

Please elicit a history to determine whether the subject currently has or has experienced any of the following diseases/conditions (new or exacerbation of existing) since the last review.

Disease, condition or problem	Approximately when did they FIRST notice this condition?	Over the past 12 months have they seen a health care provider for this condition?	Over the past 12 months, have they been hospitalized for this condition?	Study Physician's Comments including Diagnosis

1. New or exacerbated hematologic disorders including laboratory abnormalities?
 
 No (skip to Q2)
 
 Yes
	

 
 dd mm yy 
	
No.....
 
Yes...
	
No
 
Yes: (record hospital name)
	
.....
 
.....
 
.....

2. New malignancies including skin cancer?
 
 No (skip to Q3)
 
 Yes
	

 
 dd mm yy 
	
No.....
 
Yes...
	
No
 
Yes: (record hospital name)
	
.....
 
.....
 
.....


3. Exposure to possible therapeutic or environmental mutagenic agents including radiotherapy or chemotherapy?
 
 No (skip to Q4)
 
 Yes
	

 
 dd mm yy 
	
No.....
 
Yes...
	
No
 
Yes: (record hospital name)
	
.....
 
.....
 
.....

Disease, condition or problem	Approximately when did they FIRST notice this condition?	Over the past 12 months have they seen a health care provider for this condition?	Over the past 12 months, have they been hospitalized for this condition?	Study Physician's Comments including Diagnosis

4. New or exacerbated immunologic/rheumatologic disorder
 
 No (skip to Q5)
 
 Yes
	
 ____-____-____ dd mm yy 
	
No....
 
Yes...
	
No
 
Yes: (record hospital name)
	
.....
 
.....

5. New or exacerbated neurologic disorder
 
 No (skip to Q6)
 
 Yes
	
 ____-____-____ dd mm yy 
	
No....
 
Yes...
	
No
 
Yes: (record hospital name)
	
.....
 
.....

6. Adverse Events other than covered above?
 
 No (skip to PART B)
 
 Yes (complete Q7)
	
 ____-____-____ dd mm yy 
	
No....
 
Yes...
	
No
 
Yes: (record hospital name)
	
.....
 
.....

Disease, condition or problem	Approximately when did they FIRST notice this condition?	Over the past 12 months have they seen a health care provider for this condition?	Over the past 12 months, have they been hospitalized for this condition?	Study Physician's Comments including Diagnosis

7. Was this adverse event serious?
 
 No (skip to PART B)
 
 Yes (complete Q8)
 
Physician must complete SAE Notification Form
	
 ____-____-____ dd mm yy 
	
No.....
 
Yes...
	
No
 
Yes: (record hospital name)
	
.....
 
.....
 
.....

8. For any serious adverse events, list new medications or treatments etc
				

PART B: Contact Information

1. Please read subject current address and phone contact details. Is contact information correct?

Yes (skip to Q2)

No: Record updated contact details:
.....
.....

2. Please read name, address and phone contact details for subjects NOMINATED SECONDARY CONTACT PERSON. Is contact information correct?

Yes (skip to PART C)

No: Record updated contact details:
.....
.....

PART C: Further Follow-Up

1. Do any findings noted during the interview warrant review of the subject's medical records?

No (skip to Q2)

Yes: specify details:
.....

2. Do any findings noted during the clinical history interview warrant further safety testing?

No (skip to Q3)

Yes: specify details:
.....

3. Is authorization for the release of medical records to be obtained?

No

Yes: specify details:
.....

Investigator's Signature: _____

Date: |_|_|-|_|_|_|-|_|_|

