10.1 Adverse Event Definitions and Classifications[†]

Adverse Event

An adverse event is any untoward medical occurrence in a clinical study subject administered a pharmaceutical product. An adverse event does not necessarily have a causal relationship with the treatment. An adverse event can therefore be any unfavorable and unintended sign (including an abnormal finding), symptom, or disease temporally associated with the use of a medicinal (investigational) product, whether or not related to the medicinal (investigational) product. (Definition per International Conference on Harmonisation [ICH]). This includes any occurrence that is new in onset or aggravated in severity or frequency from the baseline condition, or abnormal results of diagnostic procedures, including laboratory test abnormalities.

Note: The sponsor collects adverse events starting with the signing of the informed consent until completion of the subject's last study-related procedure.

Serious Adverse Event

A serious adverse event (SAE) as defined by ICH is any untoward medical occurrence that at any dose meets any of the following conditions:

- results in death;
- is life-threatening (the subject was at risk of death at the time of the event. It does not refer to an event that hypothetically might have caused death if it were more severe);
- requires inpatient hospitalisation or prolongation of existing hospitalisation;
- results in persistent or significant disability/incapacity;
- is a congenital anomaly/birth defect.

Medical and scientific judgment should be exercised in deciding whether expedited reporting is also appropriate in situations other than those listed above; for example, important medical events may not be immediately life-threatening or result in death or hospitalisation but may jeopardize the subject or may require intervention to prevent one of the outcomes listed in the definition above. Any adverse event is considered a serious adverse event if it is associated with clinical signs or symptoms judged by the investigator to have a significant clinical impact.

Any event requiring hospitalization (or prolongation of hospitalization) that occurs during the course of a subject's participation in a clinical study must be reported as a serious adverse event, except hospitalizations for:

- social reasons in the absence of an adverse event;
- surgery or procedure planned before entry into the study (must be documented in the source documentation and CRF)

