10.2 Procedures

NON-SERIOUS ADVERSE EVENTS

Non-serious adverse events must be recorded using medical terminology in the source document and in the case report form if they have a possible, probable or very likely suspect association to the study drug.

SERIOUS ADVERSE EVENTS

All adverse events meeting the definition of serious, regardless of severity or presumed relationship, must be recorded using medical terminology in the source document and in the case report form. Only SAEs that are “possibly”, “probably” or “very likely” related to the study drug must be reported using the Sponsor Serious Adverse Event Form within 24 hours of knowledge of the event. Exceptions to this include:

- Death, regardless of the cause, is considered a reportable SAE;
- Malignancy (except Basal Cell or Squamous Cell Carcinomas), regardless of causality, is considered a reportable SAE.

Whenever possible, diagnoses should be given when signs and symptoms are due to a common etiology (e.g. cough, runny nose, sneezing, sore throat, and head congestion should be reported as “upper respiratory infection”). Investigators must record in the CRF their opinion concerning the relationship of the SAE to study therapy. All measures required for serious adverse event management must be recorded in the source document.

OZ1: Clinical Protocol OZ1-HV1-202 Amendment 4; 07 June 2017

Subjects (or their designees, if appropriate) must be provided with a “study card” indicating the name of the investigational product, the study number, the investigator’s name, and a 24-hour emergency contact number.

All reportable SAEs occurring during the study period must be reported to the appropriate sponsor contact person by investigational staff within 24 hours of their knowledge of the event. If the SAE is a death or a life threatening event the Investigator must notify the Sponsor immediately by both telephone and FAX.

Information regarding serious adverse events will be transmitted to the sponsor using the Sponsor Serious Adverse Event Form, which must be signed by a member of the investigational staff. The initial report of a serious adverse event may be made by facsimile (fax) or telephone. It is preferable that serious adverse events be reported via fax. Subsequent to a telephone report of a serious adverse event, a Serious Adverse Event Form must be completed by the investigational staff and transmitted to the sponsor within 24 hours.

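### Telephone questionnaire (Protocol Appendix 2): the four targeted event questions never reach the seriousness prompt, and the 12-month columns conflict with the form's own recall period

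*Protocol*

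**What the plan says.** Protocol Sections 4 and 7.1 let a telephone interview stand in for a clinic visit, including the End-of-Study visit. Appendix 2 is the script, and Protocol Section 12.5 treats it, alongside the CRF, as a form on which data are entered.

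Part A has five targeted questions: haematologic disorders (Q1), new malignancies (Q2), mutagen exposure (Q3), immunologic/rheumatologic disorders (Q4) and neurologic disorders (Q5). Q6 then asks about "Adverse Events other than covered above". A Yes to Q6 leads to Q7, which asks whether that event was serious and states "Physician must complete SAE Notification Form". A No to Q6 goes straight to Part B.

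On recall, the instructions state "All questions refer to the time since the since the last study visit or interview". One column heading, repeated for every item, reads "Over the past 12 months, have they been hospitalized for this condition". The neighbouring column on seeing a health care provider uses the same 12-month period.

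Protocol Section 10.1 lists among its seriousness criteria an event that "requires inpatient hospitalisation or prolongation of existing hospitalisation". Section 10.2 says "All adverse events meeting the definition of serious, regardless of severity or presumed relationship, must be recorded" in the source document and CRF. Non-serious events go into the CRF only if related. SAP Section 8.2 takes its adverse event tables from the CRF adverse event section.

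**The concern.** The form asks about seriousness for residual events but not for the conditions this follow-up exists to detect. Insertional oncogenesis is a stated objective, and the targeted disorders are the ones each visit must record in detail. An interviewer who follows the printed skips finishes Q1 to Q5 without being asked whether any reported event was serious. A Yes under hospitalisation normally meets a Section 10.1 criterion, yet in those rows it triggers nothing.

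The recall conflict affects the same information. The hospitalisation column is the only seriousness cue in the targeted rows. If contacts are more than 12 months apart, a hospitalisation 14 months before the call but after the last contact is answered No. At semi-annual spacing the error runs the other way, and a hospitalisation already covered at the previous review can be recorded again.

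At stake is whether a serious targeted event learned of by telephone reaches the CRF adverse event section, and so Tables 14.3.x, with its seriousness recorded.

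**Working it through.** **Routing.** Inputs are the printed skip instructions in Appendix 2, Part A.

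- Q1 to Q5: No skips to the next question. Yes has no onward pointer, and the general instruction asks only for the sub-sections and comments.
- Q6: Yes leads to Q7; No leads to Part B.
- Q7: Yes leads to Q8 (treatments for serious events); No leads to Part B. Q8 therefore cannot rescue an event that never reached Q7.

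There are 2^6 = 64 answer patterns for Q1 to Q6. Those with at least one Yes among Q1, Q2, Q4 and Q5 number (2^4 − 1) × 2 (Q3) × 2 (Q6) = 60. In the 30 with Q6 = No, Q7 is never shown. In the other 30, Q7 is shown but refers to the Q6 event. These are counts of patterns on the form, not frequencies of patients.

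Q3 asks about an exposure, so it needs no seriousness prompt. For Q2 only the reminder is missing, because Section 10.2 makes malignancy, other than basal or squamous cell carcinoma, reportable regardless of causality.

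**Recall.** Inputs are the annual interval of 12 months ± 12 weeks and the semi-annual interval of 6 months ± 6 weeks (Protocol Section 4). Visits are anchored to the infusion date (Section 7.1), so an early visit followed by a late one adds both windows. Taking 12 months as 52 weeks:

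- uncovered = max(0, gap − 52)
- overlap with the previous review period = max(0, 52 − gap)

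| Spacing of contacts | Gap (weeks) | Uncovered | Overlap |
|---|---|---|---|
| Annual, nominal | 52 | 0 | 0 |
| Annual, early then late | 52 + 12 + 12 = 76 | 24 (24/76 = 32%) | 0 |
| Annual, late then early | 52 − 24 = 28 | 0 | 24 |
| One annual contact missed, nominal | 104 | 52 (50%) | 0 |
| One annual contact missed, window extremes | 104 + 24 = 128 | 76 (76/128 = 59%) | 0 |
| Semi-annual, nominal | 26 | 0 | 26 |
| Semi-annual, window extremes | 14 to 38 | 0 | 38 to 14 |
| One semi-annual contact missed, nominal | 52 | 0 | 0 |
| One semi-annual contact missed, window extremes | 52 + 12 = 64 | 12 (12/64 = 19%) | 0 |

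The two periods agree only when the gap is exactly 12 months. The End-of-Study visit is exempt from the annual window, and a lost or withdrawn patient may re-enter up to 30 November 2017, so either can give a longer gap.

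**The case against.** The form is not the only safeguard. A study investigator makes the call, and Section 10.2 binds whatever the form asks. SAP Section 8.2 has the investigator evaluate patient-reported events, and under Protocol Section 12.6 monitors compare the CRF with source documents. Every row has a column for "Study Physician's Comments including Diagnosis", and Part C asks "Do any findings noted during the interview warrant review of the subject's medical records". All of this stands and lowers the priority. None of it asks, for a Q1, Q2, Q4 or Q5 event, whether the event was serious.

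A reader might infer that serious targeted events found by telephone vanish from the analysis. The documents do not support that. Tables 14.4.1 to 14.4.6 tabulate the same conditions by visit, and the shell has its own telephone column.

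A reader might also infer that relationship to the product goes unrecorded for telephone contacts, because Appendix 2 does not ask it. SAP Section 8.5 expects a relationship answer for the targeted items, and the Table 14.4.1 shell splits Yes into related and not related. The CRF is not among the documents, so at most this needs checking.

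It is also tempting to say that the targeted rows ask about only one of the five seriousness criteria listed in Section 10.1. That overstates the gap: a patient cannot report their own death, which has its own reporting rule, and abnormal pregnancy outcomes have a separate procedure.

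Finally, the recall percentages are shares of calendar time at assumed spacings, not shares of events missed. No window is stated for the call itself, so 76 weeks illustrates the gap and does not bound it. The conditions and their first onset are still asked for the whole interval. The semi-annual rows concern past calls only, since SAP Section 1.1 puts the last subject's year-10 visit in February 2016.

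**Conclusion.** Both defects stand on the printed text. Q6 is the only route to the form's seriousness question and SAE prompt, so four of the five targeted questions bypass it. The two 12-month columns contradict the form's own recall period.

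The consequence is incomplete seriousness capture in Tables 14.3.x for telephone contacts, not loss of the conditions from the report. That limit assumes the CRF clinical history is completed for telephone contacts as SAP Section 8.5 describes. The number of telephone contacts, and how often gaps exceed 12 months, are not given, so no event count can be attached. Priority is minor, but the repair is specific and cheap enough to be worth making.

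**What to change.** 1. **Protocol Appendix 2.** Route each Yes in Q1, Q2, Q4, Q5 and Q6 to the Q7 seriousness question and its SAE-form prompt. In both columns, replace the 12-month wording with *Since the last study visit or interview*. Add a relationship item only if the CRF does not already capture the SAP Section 8.5 relationship answer for telephone contacts.
2. **SAP Section 4.** At the Data Review Meeting, take the telephone-flagged Yes answers in Listing 16.2.12 for the haematologic, malignancy, immunologic/rheumatologic and neurologic items, and check them against Listings 16.2.8.2 and 16.2.8.3. Leave out mutagen exposure and biopsy. Query an unmatched entry only if it is a malignancy, is marked possibly related, has a recorded hospitalisation or other sign of seriousness, or has no documented seriousness assessment. Without this limit the check would query non-serious unrelated events, which are correctly absent from the adverse event listings.

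The cost of the first change is a short amendment with ethics committee approval and slightly longer calls, and it helps only contacts up to 30 November 2017. The second adds a short instruction to the SAP and a few data queries. It uses listings already planned for the meeting, with the telephone flag already specified for Listing 16.2.12, and it also covers past calls.
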